5.1.3 Management of Asymptomatic Lipase and/or Amylase Elevations

Some patients treated with GDC-0032 have experienced asymptomatic lipase and/or amylase elevations in blood tests without any clinical or radiographic symptoms of

pancreatitis or another clear etiology for the abnormal laboratory values. Upon discussion with the Medical Monitor and after a risk-benefit assessment, investigators can consider continuing GDC-0032 therapy in such patients at the same dose or one dose level lower. Investigators should have a low threshold for interrupting GDC-0032 for any concerning clinical gastrointestinal toxicities.

5.1.4 Management of Other Clinically Significant Adverse Events

See [Table 7](#) for the dose modifications for other clinically significant adverse events.

Table 7 GDC-0032 Dose Delay and Modification Guidelines for Other Clinically Significant Adverse Events

Grade	GDC-0032/ placebo
Grade 3: first event	
 • Hold GDC-0032/placebo until Grade ≤ 1. • Consider restarting at next lower dose.
Grade 3: recurrent	
 • Hold GDC-0032/placebo until Grade ≤ 1.
Grade 4: non-life-threatening	
 • Restart at next lower dose.
Grade 4: life-threatening	
 • Permanently discontinue GDC-0032/placebo.

5.1.5 General Guidance for Dose Modifications and Delays for Letrozole

The letrozole dose level cannot be modified. In general, the investigator can consider continuing letrozole if it is not thought to be letrozole-related.

All dose modifications should be based on the adverse event requiring the greatest modification and should be properly documented in the source documents.

5.1.6 Management of Increases in QT Interval

Study drug should be discontinued in patients who develop any of the following, unless there is a clear alternative cause for the changes:

1. Sustained (at least two ECG measurements >30 minutes apart) QTcF that is >500 msec and >60 msec longer than the baseline value
2. Sustained absolute QTcF that is > 515 msec
3. An episode of torsades de pointes or a new ECG finding of clinical concern

Of note, if there is a new intraventricular conduction block, the increase in QRS complex duration should be subtracted from the QTcF change, as this represents an increase in QTcF unrelated to alterations in repolarization. Also of note, it is not uncommon to record arrhythmias such as non-sustained ventricular tachycardia, supraventricular tachycardia, pauses, or atrial fibrillation in healthy volunteers receiving placebo during periods of extended ECG monitoring. Therefore, it is critical that expert electrophysiologic advice be sought to confirm any ECG changes and to ascertain the

likelihood of a drug-induced arrhythmia versus the background occurrence of this arrhythmia. In such a situation, saving all available ECG data is highly suggested.

Management of patients with sustained QTcF prolongation should include close monitoring, with ECGs repeated at least hourly until two successive ECGs show resolution of the findings, correction of any electrolyte abnormalities, and possible discontinuation of other concomitant medications that are known to prolong the QT interval. Consultation with a cardiologist or electrophysiologist is recommended, to help in the management of such patients.

In rare circumstances, it may be acceptable to resume study drug, at a lower dose, provided that any ECG abnormalities have resolved and the patient is appropriately monitored. Clinical judgment should be applied.

5.1.7 Safety Monitoring for Letrozole

Letrozole is a nonsteroidal AI indicated for first line treatment of hormone receptor positive, locally advanced, or metastatic breast cancer in postmenopausal women. Letrozole is also indicated for adjuvant treatment in postmenopausal hormone-receptor positive patients and for the treatment of advanced breast cancer in postmenopausal women with disease progression following anti-estrogen therapy.

The most frequently reported adverse events in a first line, breast cancer clinical trial with letrozole were bone pain, hot flushes, back pain, nausea, arthralgia, and dyspnea. Clinically significant adverse events also include bone effects (osteoporosis and bone fractures) and hypercholesterolemia. Discontinuations for adverse events other than progression of tumor occurred in 2% of patients on letrozole. Refer to the U.S. letrozole Package Insert or SmPC for additional information.

There are no expected significant overlapping toxicities between letrozole and GDC-0032. Routine safety monitoring and periodic laboratory tests for the letrozole and GDC-0032 combination will occur throughout the study.

5.2 SAFETY PARAMETERS AND DEFINITIONS

Safety assessments will consist of monitoring and recording adverse events, including serious adverse events and adverse events of special interest; measurement of protocol-specified safety laboratory assessments; measurement of protocol-specified vital signs; and other protocol-specified tests that are deemed critical to the safety evaluation of the study.

Certain types of events require immediate reporting to the Sponsor, as outlined in Section [5.4](#).

5.2.1 Adverse Events

According to the ICH guideline for Good Clinical Practice, an adverse event is any untoward medical occurrence in a clinical investigation subject administered a pharmaceutical product, regardless of causal attribution. An adverse event can therefore be any of the following:

- Any unfavorable and unintended sign (including an abnormal laboratory finding), symptom, or disease temporally associated with the use of a medicinal product, whether or not considered related to the medicinal product
- Any new disease or exacerbation of an existing disease (a worsening in the character, frequency, or severity of a known condition), except as described in Section [5.3.5.9](#)
- Recurrence of an intermittent medical condition (e.g., headache) not present at baseline
- Any deterioration in a laboratory value or other clinical test (e.g., ECG, X-ray) that is associated with symptoms or leads to a change in study treatment or concomitant treatment or discontinuation from study drug
- Adverse events that are related to a protocol-mandated intervention, including those that occur prior to assignment of study treatment (e.g., screening invasive procedures such as biopsies)

5.2.2 Serious Adverse Events (Immediately Reportable to ABCSG)

A serious adverse event is any adverse event that meets any of the following criteria:

- Fatal (i.e., the adverse event actually causes or leads to death)
- Life threatening (i.e., the adverse event, in the view of the investigator, places the patient at immediate risk of death). This does not include any adverse event that had it occurred in a more severe form or was allowed to continue might have caused death.
- Requires or prolongs inpatient hospitalization (see Section [5.3.5.10](#))
- Results in persistent or significant disability/incapacity (i.e., the adverse event results in substantial disruption of the patient's ability to conduct normal life functions)
- Congenital anomaly/birth defect in a neonate/infant born to a mother exposed to study drug
- Significant medical event in the investigator's judgment (e.g., may jeopardize the patient or may require medical/surgical intervention to prevent one of the outcomes listed above)

The terms “severe” and “serious” are not synonymous. Severity refers to the intensity of an adverse event (rated as mild, moderate, or severe, or according to NCI CTCAE criteria; see Section [5.3.3](#)); the event itself may be of relatively minor medical significance (such as severe headache without any further findings).

Severity and seriousness need to be independently assessed for each adverse event recorded on the eCRF.

Serious adverse events are required to be reported by the investigator to ABCSG safety department immediately (i.e., no more than 24 hours after learning of the event; see Section 5.4.2 for reporting instructions).

5.2.3 Adverse Events of Special Interest (Immediately Reportable to ABCSG)

Adverse events of special interest are required to be reported by the investigator to ABCSG safety department immediately (i.e., no more than 24 hours after learning of the event; see Section 5.4.2 for reporting instructions). Adverse events of special interest for this study include the following:

- Grade 4 hyperglycemia
- Grade ≥ 3 symptomatic hyperglycemia
- Grade ≥ 2 colitis or enterocolitis
- Grade ≥ 2 diarrhea
- *Grade ≥ 1 diarrhea for >2 weeks after following medical management guidelines in Section 5.1.1.4*
- Grade ≥ 3 rash
- Grade ≥ 2 pneumonitis
- Cases of potential drug-induced liver injury that include an elevated ALT or AST in combination with either an elevated bilirubin or clinical jaundice, as defined by Hy's law (see Section 5.3.5.5)
- Suspected transmission of an infectious agent by the study drug

5.3 METHODS AND TIMING FOR CAPTURING AND ASSESSING SAFETY PARAMETERS

The investigator is responsible for ensuring that all adverse events (see Section 5.2.1 for definition) are recorded on the Adverse Event eCRF and additionally reported to ABCSG safety department in case they fulfill the criteria for expedited reported in accordance with instructions provided in this section and in Section 5.4–Section 5.6.

For each adverse event recorded on the Adverse Event CRF, the investigator will make an assessment of seriousness (see Section 5.2.2 for seriousness criteria), severity (see Section 5.3.3), and causality (see Section 5.3.4).

5.3.1 Adverse Event Reporting Period

After initiation of study drug, all adverse events, regardless of relationship to study drug, will be reported until 30 days after the last dose of study drug or until the end of study visit, whichever occurs later. After this period, investigators should report any

deaths, serious adverse events, or other adverse events of concern deemed related to prior study drug treatment or study procedures (Section 5.6).

5.3.2 Eliciting Adverse Event Information

A consistent methodology of non-directive questioning should be adopted for eliciting adverse event information at all patient evaluation timepoints. Examples of non-directive questions include the following:

“How have you felt since your last clinic visit?”

“Have you had any new or changed health problems since you were last here?”

5.3.3 Assessment of Severity of Adverse Events

The adverse event severity grading scale for the NCI CTCAE, v4.0 will be used for assessing adverse event severity. Table 8 will be used for assessing severity for adverse events that are not specifically listed in the NCI CTCAE.

Table 8 Adverse Event Severity Grading Scale

Grade	Severity
1	Mild; asymptomatic or mild symptoms; clinical or diagnostic observations only; or intervention not indicated
2	Moderate; minimal, local, or non-invasive intervention indicated; or limiting age-appropriate instrumental activities of daily living ^a
3	Severe or medically significant, but not immediately life-threatening; hospitalization or prolongation of hospitalization indicated; disabling; or limiting self-care activities of daily living ^{b,c}
4	Life-threatening consequences or urgent intervention indicated ^d
5	Death related to adverse event ^d

NCI CTCAE = National Cancer Institute Common Terminology Criteria for Adverse Events.

Note: Based on the most recent version of NCI CTCAE (v 4.0), which can be found at: http://ctep.cancer.gov/protocolDevelopment/electronic_applications/ctc.htm.

^a Instrumental activities of daily living refer to preparing meals, shopping for groceries or clothes, using the telephone, managing money, etc.

^b Examples of self-care activities of daily living include bathing, dressing and undressing, feeding one's self, using the toilet, and taking medications, as performed by patients who are not bedridden.

^c If an event is assessed as a "significant medical event," it must be reported as a serious adverse event (see Section 5.4.2 for reporting instructions), per the definition of serious adverse event in Section 5.2.2.

^d Grade 4 and 5 events must be reported as serious adverse events (see Section 5.4.2 for reporting instructions), per the definition of serious adverse event in Section 5.2.2.

5.3.4 Assessment of Causality of Adverse Events

Investigators should use their knowledge of the patient, the circumstances surrounding the event, and an evaluation of any potential alternative causes to determine whether or not an adverse event is considered to be related to the study drug, indicating "yes" or "no" accordingly. The following guidance should be taken into consideration (see also [Table 9](#)):

- Temporal relationship of event onset to the initiation of study drug
- Course of the event, considering especially the effects of dose reduction, discontinuation of study drug, or reintroduction of study drug (where applicable)
- Known association of the event with the study drug or with similar treatments
- Known association of the event with the disease under study
- Presence of risk factors in the patient or use of concomitant medications known to increase the occurrence of the event
- Presence of non-treatment-related factors that are known to be associated with the occurrence of the event

Table 9 Causal Attribution Guidance

Is the adverse event suspected to be caused by the study drug on the basis of facts, evidence, science-based rationales, and clinical judgment?	
YES	There is a plausible temporal relationship between the onset of the adverse event and administration of the study drug, and the adverse event cannot be readily explained by the patient's clinical state, intercurrent illness, or concomitant therapies; and/or the adverse event follows a known pattern of response to the study drug; and/or the adverse event abates or resolves upon discontinuation of the study drug or dose reduction and, if applicable, reappears upon re-challenge.
NO	Adverse events will be considered related, unless they fulfill the criteria as specified below. Evidence exists that the adverse event has an etiology other than the study drug (e.g., preexisting medical condition, underlying disease, intercurrent illness, or concomitant medication); and/or the adverse event has no plausible temporal relationship to administration of the study drug (e.g., cancer diagnosed 2 days after first dose of study drug).

For patients receiving combination therapy, causality will be assessed individually for each protocol-mandated therapy.

5.3.5 Procedures for Recording Adverse Events

Investigators should use correct medical terminology/concepts when recording adverse events on the Adverse Event eCRF. Avoid colloquialisms and abbreviations.

Only one adverse event term should be recorded in the event field on the Adverse Event eCRF.

If known, a diagnosis should be recorded on the Adverse Event eCRF rather than individual signs and symptoms (e.g., record only liver failure or hepatitis rather than jaundice, asterixis, and elevated transaminases). However, if a constellation of signs and/or symptoms cannot be medically characterized as a single diagnosis or syndrome at the time of reporting, each individual event should be recorded on the Adverse Event eCRF. If a diagnosis is subsequently established, all previously reported adverse events based on signs and symptoms should be nullified and replaced by one adverse event report based on the single diagnosis, with a starting date that corresponds to the starting date of the first symptom of the eventual diagnosis.

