3.4.2 Safety Outcome Measures

The safety and tolerability of GDC-0032 will be assessed using the following primary safety outcome measures:

- Incidence, nature, and severity of adverse events graded according to NCI CTCAE, v4.0
- Incidence and type of adverse events leading to dose discontinuation, modification, or delay
- Serious adverse events
- Protocol-defined adverse events of special interest
- Clinically significant changes in vital signs and in clinical laboratory results during the adverse event reporting period (see [Section 5.3.1](#))

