5.1.1.4 Management of Gastrointestinal Toxicity

5.1.1.4.1 Management of Diarrhea and Colitis

Patients should be closely monitored for gastrointestinal symptoms (e.g., nausea, vomiting, diarrhea, abdominal pain, stomatitis, and changes in stool, including checking for blood in stool if clinically indicated). Patients should be advised to inform the investigator if any diarrhea occurs, even if it is mild. *Weekly patient contact (e.g., telephone call) for all events of diarrhea Grades ≥ 1 is recommended to closely follow until resolution of symptoms.* Gastrointestinal symptoms should be managed per protocol guidelines and institutional standard of care. For example, prompt management of diarrhea with antidiarrheal medications should be implemented. Because of the approximately 40-hour half-life of GDC-0032, investigators should hold GDC-0032/*placebo* for Grade ≥ 2 diarrhea.

Steroid-responsive diarrhea and colitis have been difficult to distinguish in patients treated with GDC-0032. All cases of colitis have been reversible with corticosteroid treatment. Prompt initiation of corticosteroids for persistent diarrhea despite antidiarrheal treatment can decrease the severity of the diarrhea and prevent the need

for hospitalizations. Patients who develop severe steroid-responsive diarrhea usually have been on GDC-0032 treatment for at least 2 months, with an average onset between 4 and 6 months of treatment. A stool culture is helpful in identifying concurrent infections, and patients have been successfully treated with concurrent steroids and appropriate antibiotics if needed.

If a patient is being treated with corticosteroids, total parenteral nutrition is discouraged as this increases the risk for severe hyperglycemia. Discontinuation of nonsteroidal inflammatory medications or other medications that exacerbate colitis are also recommended during colitis episodes.

Perforated duodenal ulcer has been observed in 2 patients (one patient at 6 mg *capsule* in combination with letrozole; another patient at 6 mg *capsule* in combination with fulvestrant). Appropriate caution should be taken with the administration of medications such as aspirin, nonsteroidal anti-inflammatory drugs, and corticosteroids that can increase the risk of gastritis, peptic ulcers, or gastrointestinal perforation.

Specific dose modification and management guidelines for diarrhea and colitis are provided in [Table 5](#).

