Table 5 GDC-0032 Dose Modification and Management Guidelines for Diarrhea and Colitis

Grade of Diarrhea	Dose Modification and Management Guidelines
Grade 1	
 • Manage per institutional standard of care that includes antidiarrheals.^a • For persistent Grade 1 diarrhea occurring after Cycle 2, recommend evaluation for infectious causes via stool culture.^b For noninfectious diarrhea, consider colonoscopy to evaluate for colitis. • For any grade of diarrhea (≥ 1), contact patient at least weekly to monitor until resolution of symptoms. If symptoms persist beyond 2 weeks despite antidiarrheal treatment (e.g., loperamide), escalate to Grade 2 management.
Grade 2	
 • Hold GDC-0032/placebo and initially manage with antidiarrheals.^a • Obtain stool culture for infectious workup.^b Infections (e.g., Clostridium difficile, enteric bacteria, CMV) should be treated with the appropriate antibiotic. • For persistent Grade 2 non-infectious diarrhea lasting longer than 48 hours despite treatment with antidiarrheals, treat with oral corticosteroids (20–40 mg prednisone QD starting dose with taper) or budesonide 9 mg PO QD. • If Grade 2 diarrhea occurred after Cycle 2, was a recurrent episode, or improved with corticosteroid treatment, resume GDC-0032/placebo treatment at one dose level lower upon improvement to Grade ≤ 1 and after completion of corticosteroid treatment.

Grade of Diarrhea	Dose Modification and Management Guidelines
	
 • If Grade 2 diarrhea occurred before Cycle 2, did not require corticosteroid treatment, and was an initial episode, resume GDC-0032/placebo treatment at the same dose upon improvement to Grade ≤ 1. • For Grade 2 colitis, resume GDC-0032/placebo treatment at one dose level lower upon improvement to Grade ≤ 1 and after completion of corticosteroid treatment. • If Grade 2 diarrhea does not improve after 48 hours of corticosteroid treatment, a colonoscopy is recommended to evaluate for other causes of diarrhea (e.g., CMV colitis).

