6.5 SAFETY ANALYSES

Safety analyses will include all patients who received at least one dose of study treatment, with patients allocated to the treatment arm associated with the regimen actually received.

Safety will be assessed through summaries of adverse events, changes in laboratory test results, changes in vital signs, and letrozole and GDC-0032 exposure.

Verbatim descriptions of adverse events will be mapped to thesaurus terms. Adverse event data will be listed by study site, treatment arm, patient number, and study day, severity, relationship to study drug, outcome, and action taken with the study treatments. Events occurring on or after treatment on Day 1 of Week 1 will be summarized by thesaurus term, appropriate thesaurus levels, and NCI CTCAE, v4.0 grade. Serious adverse events, including deaths, will be listed separately and will be summarized.

Relevant laboratory and vital sign (heart rate, blood pressure, and temperature) data will be displayed by time, with NCI CTCAE, v4.0 Grade 3 and 4 values identified, where appropriate. Additionally, all laboratory data will be summarized in tables by NCI CTCAE, v4.0 grade.

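### Section 5.3.5 nullifies diarrhea that is itself an event of special interest once colitis is diagnosed, so its grade and duration drop out of the diarrhea summaries

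*Protocol*

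**What the plan says.** **Recording rule (5.3.5).** Symptoms are recorded individually until a diagnosis is known. Once it is, "all previously reported adverse events based on signs and symptoms should be nullified and replaced by one adverse event report", "with a starting date that corresponds to the starting date of the first symptom of the eventual diagnosis". No event type is exempted.

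**Events of special interest (5.2.3).** The list has separate entries for "Grade ≥ 2 colitis or enterocolitis", for "Grade ≥ 2 diarrhea", and for diarrhea of Grade 1 or higher that persists beyond 2 weeks despite the management guidelines. The Version 4 summary of changes shows that the diarrhea threshold was lowered from Grade 3 to Grade 2 and that the 2-week entry was added.

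**Use in the analysis.** Section 3.4.2 includes "Protocol-defined adverse events of special interest" among the primary safety outcome measures, beside the incidence, nature and severity of adverse events. Section 6.5 states: "Events occurring on or after treatment on Day 1 of Week 1 will be summarized by thesaurus term", with thesaurus levels and CTCAE grade.

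**How the two conditions meet.** Section 5.1.1.4.1 says: "Steroid-responsive diarrhea and colitis have been difficult to distinguish in patients treated with GDC-0032". Table 5 in that section, for persistent Grade 1 diarrhea, says: "For noninfectious diarrhea, consider colonoscopy to evaluate for colitis". It also recommends colonoscopy for Grade 2 or 3 diarrhea that does not improve on corticosteroids.

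**Neighboring rules.** Section 5.3.5.1 generally records secondary events under their primary cause. It excepts severe or serious secondary events and asks for separate records when the association is unclear. Section 5.3.5.2 keeps the worst severity within a persistent event's record.

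**The concern.** Diarrhea is usually a symptom of colitis, and the protocol's own work-up for persistent diarrhea includes looking for colitis. Two parts of the protocol therefore pull against each other. Section 5.2.3 makes diarrhea reportable in its own right at a low threshold. Section 5.3.5 tells the site to remove that record when the work-up finds the cause.

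The loss happens when the event is recorded. A combined diarrhea-or-colitis row in the tables can bring back the patient if colitis is recorded, but not the grade and duration of a diarrhea event that no longer exists among the reported events. Version 4 was prompted by suboptimally managed diarrhea, including one case that resulted in colitis, so this information is what the amendment set out to capture. With about 110 sites and no explicit rule, similar episodes may also be recorded differently from site to site.

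**Working it through.** **Step 1. Apply the rules to three illustrative patients.**

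| Reported first | Diagnosed later | Record left under 5.3.5 | Result |
|---|---|---|---|
| Grade 2 diarrhea | Grade 2 colitis | One Grade 2 colitis event, dated from first symptom | Still of special interest, but absent from the diarrhea count |
| Grade 1 diarrhea for more than 2 weeks | Grade 1 colitis | One Grade 1 colitis event | Matches no colitis entry in 5.2.3 and leaves the special-interest set |
| Grade 3 diarrhea | Grade 2 colitis | Unclear | Nullified under 5.3.5, or kept if read under 5.3.5.1 as a severe secondary event |

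Table 5 has separate instructions for Grade 2 diarrhea and Grade 2 colitis, so the terms are graded separately. Section 5.3.5 does not say that the replacing record inherits the diarrhea grade.

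**Step 2. Reproduce the protocol's colitis rate.** Section 3.3.7 gives 10 of 160: 10/160 = 6.25%, in agreement with the stated 6.2%.

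**Step 3. Expected number in this trial.** Inputs: about 330 patients randomized 1:1 (3.1), so 330/2 = 165 on GDC-0032; a maximum of 16 weeks of GDC-0032, or 112 days (3.1); onset from about Day 82 to Day 248 (3.3.7); latest scheduled surgery on Day 126 (Appendix 1), plus 4 weeks = Day 154. Assumptions: the earlier rate applies here, each colitis case had a reportable diarrhea record, and onset is uniform over Days 82 to 248.

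- Ceiling, with no allowance for timing: 165 × 0.0625 = 10.3 patients.
- By Day 112: share (112 − 82)/(248 − 82) = 30/166 = 0.181; 10.3 × 0.181 = 1.9 patients.
- By Day 154: share (154 − 82)/166 = 0.434; 10.3 × 0.434 = 4.5 patients.

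**Step 4. Effect on the diarrhea rates.** Section 1.7.1 gives related diarrhea rates with letrozole of 67% (any grade) and 11% (Grade 3 or 4), from 27 patients. Assumed here, these are 165 × 0.67 = 110.6 and 165 × 0.11 = 18.2 patients.

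| Nullified | Any grade: share lost, rate shown | Grade 3 or 4, if every nullified case was Grade 3 or 4: share lost, rate shown |
|---|---|---|
| 1.9 | 1.7%, 65.8% | 10%, 9.8% |
| 4.5 | 4.1%, 64.3% | 25%, 8.3% |
| 10.3 | 9.3%, 60.8% | 57%, 4.7% |

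The last column is an extreme. It is zero if sites keep all Grade 3 or 4 diarrhea as severe secondary events.

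**The case against.** The case against has several parts, and much of it stands.

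**Patients are mostly reclassified.** Grade 2 or higher colitis is itself a special-interest event, and the replacing record keeps the first-symptom date. Severe diarrhea without a colitis diagnosis stays under diarrhea. A reader might infer that the safety tables lose the worst patients; the documents do not support that. Only the step from prolonged Grade 1 diarrhea to Grade 1 colitis leaves the special-interest set, and no frequency is given for it.

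**Section 5.3.5.1 may keep some records.** It protects severe or serious secondary events and asks for separate records when the link is unclear, which 5.1.1.4.1 suggests will be common. This stands in part. The protocol does not say whether presenting diarrhea is a secondary event of colitis or a symptom to be nullified. Even on a generous reading, non-serious Grade 2 or prolonged Grade 1 diarrhea is not clearly protected once it is linked to colitis.

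**The information survives elsewhere.** Special-interest diarrhea will already have gone to the safety department (5.4.2), a changed diagnosis is follow-up to that report (5.4), and the audit trail is kept (7.1). This is true, but the summaries in 6.5 are built from reported events.

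**First-symptom dating is defensible.** A reader might call it backdating. It is an explicit and consistent convention; dating from objective evidence would tie onset to when a colonoscopy happens to be scheduled.

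**The numbers are small.** Most earlier colitis was at the 9-mg capsule level or higher, and neither endocrine-combination cohort lists Grade 3 or 4 colitis (1.7.1). This stands, and the true count may be below the figures above.

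**Conclusion.** The point holds as a gap in the recording rule. Nothing in 5.3.5 exempts special-interest diarrhea, and 5.3.5.1 does not clearly fill the gap. Followed literally, the diarrhea summaries lose the record, grade and duration for patients later diagnosed with colitis, and one combination drops out of the special-interest set.

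The likely size is about 2 to 5 of 165 GDC-0032 patients, with about 10 as a ceiling. These figures rest on the earlier colitis rate, uniform onset, and a reportable diarrhea record before every colitis case. The effect on any-grade diarrhea is slight. The effect on Grade 3 or 4 diarrhea could be noticeable, but only if most nullified cases had reached that grade and sites did not keep them under 5.3.5.1.

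Three further inferences are not supported. That almost all the loss falls in the GDC-0032 arm is plausible, but no colitis rate on placebo or letrozole alone is given. The single-agent Grade 3 or 4 rates of 6% for colitis and 3% for diarrhea (1.7.1) do not show such replacement, because that study's recording rules are not described. What the iDMC would see depends on its charter, which is not shown.

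**What to change.** Add one sentence to 5.3.5: diarrhea meeting a 5.2.3 criterion is not nullified when colitis or enterocolitis is later diagnosed; it keeps its own grade and dates and is linked to the colitis record. Keep the existing first-symptom dating for colitis. Carry the exemption into the eCRF completion guidance.

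In the safety summaries, count patients with diarrhea, with colitis, and with either, once each by worst grade. This table can sit in the SAP, and its absence from the protocol is not a defect. It does need the records that the exemption preserves.

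No clinical rule changes. The downside is small: one episode can appear as two linked events in event-level listings, and the patient-level row for either condition avoids double counting.
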